9.7 Pre-discharge Follow-up

Subjects are required to stay in the hospital for a minimum of 4 hours post-procedure. Post-procedure assessment must occur during the index procedure hospitalization prior to hospital discharge or at 7 days post index procedure, whichever is sooner. The evaluation must include:

- TTE is required to surveil for pericardial effusion. The study must be performed at a minimum of 4 hours from the end of the procedure (removal of the access sheath).
- A neurological assessment (NIHSS and mRS) to evaluate neuro status of subject. If the
 assessment is indicative of a potential neurological deficit, further evaluation by a boardcertified neurologist or designee (e.g., neurology fellow) must be performed.
- Adverse event assessment

Prior to hospital discharge, research staff should review the follow-up requirements with the subject to ensure compliance with the subsequent follow-up assessment.

9.8 7-day Follow-up + 2 Days (Telehealth Visit)

All subjects must undergo a follow-up assessment on days 7 to 9 post-procedure to enable timely documentation of safety endpoint events.

If the subject has not yet been discharged from the index procedure hospitalization at day 7 post-procedure, the 7-day follow-up may be conducted in-hospital, and no separate telehealth visit is necessary. In-hospital/clinic visit will satisfy the telehealth visit, if appropriate.

The 7-day follow-up assessment must include:

 Questionnaire for Verifying Stroke Free Status (QVSFS). If any question is answered "Yes," a formal neurologic examination and evaluation must be performed by a board-certified neurologist or clinical designee (e.g., neurology fellow).

- Current concomitant medications documentation. If DAPT has been interrupted or terminated, the stop date (and resumption date, if applicable) and the reason for interruption/termination should be recorded.
- Adverse event assessment

9.9 45-day Follow-up ± 7 Days (Telehealth Visit and Imaging)

All subjects will complete an assessment at 45 days (±7 days) post-procedure with imaging (TEE or CT) and clinical evaluation through a minimum of a telehealth visit. The 45-day follow-up visit will include the following assessments:

- Questionnaire for Verifying Stroke Free Status (QVSFS) If any question is answered "Yes," a formal neurologic examination and evaluation must be performed by a board-certified neurologist or clinical designee (e.g., neurology fellow).

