Patent Foramen Ovale	Patent foramen ovale [PFO] is a remnant of normal fetal anatomy which persists into adulthood and is defined as a communication between the left and right atria at the level of the fossa obalis. PFOs that do not warrant closure do not meet adverse event reporting criteria.
Procedure success	Defined as Technical Success without in-hospital major procedure-related complications (excluding minor device

	embolization) evaluated at hospitalization or at 7 days whichever is first.
Screen failure	Any subject that has signed informed consent but at any point during the process does not fulfill all eligibility criteria will be considered a Screen Failure.
Serious Adverse Device Effect (SADE)	A serious adverse device effect is an adverse device effect that has resulted in any of the consequences characteristic of a serious adverse event.
Serious Adverse Event (SAE)	A serious adverse event is an adverse event that: 1. Led to a death 2. Led to a serious deterioration in the health of the subject that: a. Resulted in a life-threatening illness or injury b. Resulted in a permanent impairment of a body structure or a body function c. Required in-patient hospitalization or prolongation of existing hospitalization d. Resulted in medical or surgical intervention to prevent life-threatening illness or injury or permanent impairment to body structure or a body function 3. Led to fetal distress, fetal death or a congenital abnormality or birth defect.
Systemic Embolism	Acute vascular insufficiency or occlusion of the extremities or any non-CNS organ associated with clinical, imaging, surgical/autopsy evidence of arterial occlusion in the absence of other likely mechanism (e.g., trauma, atherosclerosis, or instrumentation). When there is presence of prior peripheral artery disease, angiographic or surgical or autopsy evidence is required to show abrupt arterial occlusion.(38)
Technical Success	Defined as device success, complete closure or peri-device residual leak ≤5 mm in width on TEE, as evaluated by independent imaging core lab without device-related complications [evaluated post-procedure].
Transient ischemic attack (TIA)	NeuroARC defined (29) as transient focal neurological signs or symptoms (lasting <24 h) presumed to be due to focal brain, spinal cord, or retinal ischemia, but without evidence of acute infarction by neuroimaging or pathology (or in the absence of imaging).

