Device Related Thrombus: If thrombus is detected on the LA surface of the device on the post-procedure imaging (or any subsequent imaging), the subject should be evaluated for treatment with OAC and ASA for 4-6 weeks followed by repeat imaging. Antithrombotic therapy should be continued until confirmation of thrombus resolution has been documented on follow up imaging. Antithrombotic therapy should be individualized to the patient based on clinical (risk of anticoagulation) considerations

iii) Endocarditis Prophylaxis

Appropriate endocarditis prophylaxis is recommended for 6 months following device implantation. The decision to continue beyond 6 months is at the discretion of the principal investigator.

F. Pre-discharge Follow-up

Post-procedure assessment must occur during the index procedure hospitalization prior to hospital discharge or at 7 days post index procedure, whichever is sooner. The evaluation must include:

- Physical assessment (Weight, Pulse and Blood Pressure)
- TTE to evaluate for pericardial effusion
- Current concomitant medications documentation. If DAPT has been interrupted or terminated the stop date (and resumption date, if applicable) and the reason for interruption/termination should be recorded.
- A neurological assessment to evaluate neuro status of patient. If the assessment is indicative of a potential neurological deficit, further evaluation by a boardcertified neurologist or designee (e.g., neurology fellow) must be performed.
- Adverse event assessment

Prior to hospital discharge, research staff should review the follow-up requirements with the subject to ensure compliance with the subsequent follow-up assessment.

G. 7-day Follow-up + 2 Days (Telehealth Visit)

All subjects must undergo a follow-up assessment on day 7 to 9 post-procedure to enable timely documentation of safety endpoint events.

If the subject has not yet been discharged from the index procedure hospitalization at day 7 post-procedure, the 7-day follow-up may be conducted in-hospital, and no separate telehealth visit is necessary. In clinic visit will satisfy the telehealth visit, if appropriate.

The 7-day follow-up assessment must include:

- Questionnaire for Verifying Stroke Free Status (QVSFS). If any question is answered "Yes," a formal neurologic examination and evaluation must be performed by a board-certified neurologist or clinical designee (e.g., neurology fellow).

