- Current concomitant medications documentation. If DAPT has been interrupted or terminated, the stop date (and resumption date, if applicable) and the reason for interruption/termination should be recorded.
- Adverse event assessment.

H. 45-day Follow-up ± 7 Days (Telehealth Visit and Imaging)

All subjects will complete an assessment at 45 days (±7 days) post-procedure with imaging (TEE) \and clinical evaluation through a minimum of a telehealth visit. The 45-day follow-up visit will include the following assessments:

- Questionnaire for Verifying Stroke Free Status (QVSFS) If any question is answered "Yes," a formal neurologic examination and evaluation must be performed by a board-certified neurologist or clinical designee (e.g., neurology fellow).
- A transesophageal echocardiogram (TEE) must be performed in all subjects who left the
 index procedure with an implanted device. Subjects in whom the TEE demonstrates
 significant residual leak (>5 mm), or thrombus must undergo a repeat TEE at 6 months.
 The TEE images will be required to be uploaded in accordance with Core Lab instructions
 provided in the Study Manual of Procedures.
- Current concomitant medications documentation.
- Adverse event assessment

Prior to concluding the visit, research staff should also review the follow-up requirements with the subject to help ensure study compliance.

NOTE: For subjects who did not leave the index procedure with an implanted device and/or did not have an implant attempt, the 45-day clinic follow-up is the final required follow-up assessment for this protocol, and the TEE imaging assessment is not required. The study exit form should be completed for these subjects at this time.

I. Primary Endpoints:

i) Primary Efficacy:

Successful implantation of the LAAO Device in the LAA with acceptable position, and complete closure or peri-device residual leak ≤5 mm in width on TEE, as evaluated by independent core lab at 45 days post-procedure and without in-hospital major procedure-related complications during hospitalization or at 7 days whichever is first.

ii) Primary Safety:

A composite of Major Procedure-related complications assessed through 45 days (listed below) as adjudicated by an independent Clinical Events Committee as related to either the study device or procedure.

Major Procedure-Related Complications includes any of the following specific events with the specific definitions outlined in Appendix A for each component:

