- cardiac perforation,
- pericardial effusion requiring drainage,
- ischemic stroke,
- device embolization,
- major vascular complications

Statistical Considerations:

The sub-study is designed to demonstrate non-inferiority in CLAAS Implant success compared to the CLAAS arm of the RCT, based on the 45-day endpoint assessment. It is estimated that a total sample size of 130 subjects (including 6% attrition) is required to demonstrate non-inferiority. This estimated sample size will be verified and adjusted, if necessary, based on the observed rate of CLAAS Implant success rate in the RCT, prior to initiation of the sub-study.

J. Sample Size Determination

Subjects are enrolled in the Conscious Sedation Sub-Study when the subject has signed informed consent and has the procedure scheduled.

The Conscious Sedation Sub-Study will be analyzed by comparing subjects from the sub-study with subjects who receive the CLAAS Implant from the randomized cohort. The primary endpoint for the Sub-Study is Procedure Success at 45-days, defined as:

 successful implantation of the LAAO Device in the LAA with acceptable position, and complete closure or peri-device residual leak ≤5 mm in width on TEE, as evaluated by independent core lab [at 45 days post-procedure] and without inhospital major procedure-related complications during hospitalization or at 7 days whichever is first.

The goal of the Sub-Study will be to demonstrate non-inferiority between the two procedural techniques based on the Procedure Success at 45-day endpoint.

The endpoint will be assessed with the following non-inferiority hypothesis:

 H_0 : Pt - Pc \leq -0.10 H_A : Pt - Pc > -0.10

where Pt and Pc are the proportion of subjects with Procedure Success at 45-days in the treatment and control groups respectively and 0.10 represents the non-inferiority margin. The hypothesis will be evaluated using a one-sided 95% confidence interval for the difference in proportions based on a Farrington-Manning non-inferiority test. If the one-sided upper confidence bound for the difference is less than the non-inferiority margin, the objective will be met, and the treatment group will be non-inferior to the control group for the primary effectiveness endpoint.

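### In the conscious-sedation sub-study, the complication part of the tested endpoint stops at discharge, so the non-inferiority test could lean towards whichever group goes home earlier

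*Protocol*

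**What the plan says.** Appendix E, parts I and J, define the sub-study's primary efficacy endpoint as successful implantation in an acceptable position, adequate closure, and the subject being "without in-hospital major procedure-related complications during hospitalization or at 7 days whichever is first". Closure has a fixed time point, "as evaluated by independent core lab at 45 days post-procedure"; the complication component does not. Appendix A gives Procedure success in the RCT the same window: "evaluated at hospitalization or at 7 days whichever is first".

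This is the only sub-study endpoint with a stated hypothesis, margin and sample size: 10 points, one-sided 0.05, 122 evaluable subjects against about 600, with success expected between 90% and 95%. The sub-study is compared "with subjects who receive the CLAAS Implant from the randomized cohort", and it starts only after RCT enrolment is complete (section 8.2.3).

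On length of stay, section 9.7 says: "Subjects are required to stay in the hospital for a minimum of 4 hours post-procedure". Appendix E part A places the sub-study under all protocol requirements. Part G adds a later contact: "All subjects must undergo a follow-up assessment on day 7 to 9 post-procedure to enable timely documentation of safety endpoint events". A second primary endpoint, for safety, is "A composite of Major Procedure-related complications assessed through 45 days (listed below"). It covers the same five complication types and is adjudicated by the Clinical Events Committee, but the protocol states no hypothesis or margin for it.

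**The concern.** Take a pericardial effusion that needs drainage on day 2. In a subject still in hospital it makes the endpoint a failure. In a subject discharged on the day of the procedure, the same event leaves the endpoint a success. The length of observation is therefore set by the discharge decision, which is made after treatment by staff who know the treatment.

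Within one blinded, concurrent trial this would mostly add noise. Here the groups differ in anaesthesia technique and calendar period, and the sub-study sites are selected for their RCT experience (section 8.1, Objective 3). Any of these could change length of stay. If they do, the group discharged earlier has more of its complications left out, and the difference enters the non-inferiority test directly. Objective 3 is to show that the device can be delivered safely under sedation, so complications are central to the claim.

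**Working it through.** **1. Reproduce the plan's figure.** Inputs from Appendix E part J: n = 122 and 600, margin m = 0.10, one-sided alpha 0.05, success 0.90 to 0.95 in both groups, Farrington-Manning test. Attrition: 130 × 0.94 = 122.2.

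Power = Φ[(Δ + m − 1.645·s0)/s1], where Δ is the difference in success rates, s1 is the standard error at the assumed rates, and s0 is the standard error at the rates fitted under a difference of −0.10.

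- At 0.90: s1 = √(0.09/122 + 0.09/600) = 0.0298. The restricted rates are 0.810 and 0.910, so s0 = 0.0374. Power = Φ[(0.10 − 0.0615)/0.0298] = Φ(1.29) = 90.2%.
- At 0.95: s1 = 0.0216 and s0 = 0.0328, so power = 98.3%.

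The stated power of more than 90% reproduces. The sample size is not in question.

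**2. What the window can do.** Let c be the percentage of subjects who fail through a complication by day 7, and let fG and fS be the shares of those failures that occur before discharge under general anaesthesia and under sedation. With the same c in both groups, the net differential credited to sedation is b = c × (fG − fS). The protocol gives none of these three inputs, so the following are assumptions:

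- c = 3%, capture 90% and 80%: b = 0.3 point
- c = 5%, capture 90% and 70%: b = 1.0 point
- equal capture: b = 0
- sedated subjects staying longer: b is negative, and the test becomes harder to pass

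**3. Effect on the test.** Put sedation truly at the margin over a full 7-day window (comparator rate minus 0.10) and let the recorded sedation rate be higher by b. Exact binomial rejection rates of the Farrington-Manning test, 122 against 600:

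| b (points) | comparator 90% | comparator 95% |
|---|---|---|
| 0 | 4.7% | 4.4% |
| 0.3 | 5.5% | 5.3% |
| 1 | 7.8% | 7.9% |
| 2 | 12.4% | 13.2% |
| 3 | 18.7% | 21.0% |

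The normal approximation agrees closely: at a comparator rate of 90% it gives 5.0%, 5.8% and 8.0% for b = 0, 0.3 and 1.

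**4. Which rows are plausible.** At c = 3%, b = 2 needs a capture gap of 2/3, or 67 points. b = 3 needs every comparator complication caught and every sedation complication missed. Sections 6.3 and 6.4 report 15 + 4 + 22 + 42 = 83 CLAAS subjects with one periprocedural effusion requiring treatment, which is 1/83 = 1.2%. The lower rows are therefore extremes, and 0.3 to 1 point is the more reasonable range.

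**5. Cost in power of a fixed window.** If success stays at 90–95%, power is unchanged at 90.2–98.3%. If counting through day 7 lowers success to 89% in both groups, power is 88.4%.

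**The case against.** The strongest reply is that the direction is not shown. A reader might infer that the window favours conscious sedation, because avoiding general anaesthesia could shorten the stay. The documents do not support that as a finding: they give no discharge times for either technique, both groups share the definition, and the 4-hour minimum in section 9.7 applies equally to RCT subjects. This objection stands, and the point is limited to whichever group leaves earlier.

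Second, the 45-day safety composite counts the same complications over a fixed period, and pre-discharge echocardiography and neurological assessment are required. This limits the harm, because a late event would be visible in the report. It does not protect the non-inferiority conclusion, which rests on the other endpoint. Part J leaves final statistical details to an amendment of the analysis plan, so the lack of a safety test is not itself a fault. The endpoint definition, however, is already fixed in the protocol.

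Third, a reader might extend the point to the RCT and call its device comparison confounded. Procedure success there is a secondary endpoint reported descriptively (sections 8.5.3.2 and 14.5.3). It is not among the seven tested secondary endpoints, and the RCT primary safety endpoint runs to 12 months. No RCT conclusion depends on this window.

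Finally, an in-hospital definition is used consistently in all three places, so it is a choice and not a slip. That is fair, but within this endpoint closure is assessed at 45 days, and only the complication component ends at discharge.

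**Conclusion.** The point holds in limited form. The complication component of the only tested sub-study endpoint has a length that depends on discharge, in an unblinded and non-concurrent comparison, and a difference in length of stay would bias the test towards the group discharged earlier.

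The size rests on assumption. With a net 0.3 to 1 point of failures missed in the sedation group, the type I error rises from about 4.5% to about 5.5–8%. With equal capture there is no bias. Error rates of 12–21% follow only from differentials of 2 to 3 points, which need an implausible gap in capture at the low complication rates reported so far, and they should not be read as the expected effect. The severity is moderate: the remedy is cheap and worth making before sub-study enrolment, but the documents do not show that the planned conclusion is unsound.

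**What to change.** In Appendix E, parts I and J, count major procedure-related complications through day 7 post-procedure for every subject regardless of discharge date, and drop the in-hospital restriction. Make the same change to Procedure success in Appendix A for consistency. That is three places.

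Fill the window from the existing day 7 to 9 contact (section 9.8; Appendix E part G) and from committee adjudication. Derive the RCT CLAAS comparator with the same window. Report length of stay by group so that readers can judge whether the window mattered.

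No new visit or data item is needed for the complication count. There are two costs. Observed success may be slightly lower in both groups, with power about 88% if it falls to 89%. A descriptive secondary endpoint of an open-label RCT already under way would also change definition; reporting the current in-hospital version alongside the new one deals with that.

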8.1 Study Objectives

The pivotal trial has four objectives:

Objective 1: To evaluate the safety and effectiveness of the CLAAS System by demonstrating non-inferiority to currently marketed LAAO systems in subjects with non-valvular atrial fibrillation.

Objective 2: To demonstrate the safety of a post procedure pharmacologic antiplatelet regimen that consists of DAPT alone without concomitant anticoagulation therapy.

Objective 3: To demonstrate the ability to safely deliver the CLAAS Device using a conscious sedation protocol without general anesthesia. To investigate this objective, a separate Sub-Study will be conducted after recruitment of the RCT is complete at select, qualified sites based on the experience demonstrated in the RCT.

Objective 4: Support regulatory approval(s) in territories outside US.

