8.5.1 Primary Safety Endpoint

A composite of:

- Major Procedure-Related Complications including (identified within 12 months of procedure and adjudicated as procedure related):
 - a. cardiac perforation
 - b. pericardial effusion requiring drainage
 - c. ischemic stroke
 - d. device embolization
 - e. major vascular complications
- Major bleeding through 12 months post procedure or
- All-cause death 12 months post procedure

All definitions are provided for all components in Appendix A. All events will be adjudicated by the independent Clinical Events Committee (CEC).

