12.7 Expected Adverse Events – Risk/Benefit Analysis

The device and procedure are both associated with risks. Below is a summary of the expected risks that may occur. They are divided between those events associated with the procedure versus those associated with the CLAAS system. There may be additional risks that are unknown at this time. Risks associated with concomitant medications related to LAAO index procedure may be outlined in the informed consent form, if required by local IRB/REB/EC or equivalent.

12.7.1 Procedural Risks: The risks of delivery of the CLAAS device are like those of other procedures that require a transseptal puncture, TEE and transcatheter delivery of an implant through the venous system, across the interatrial septum, and into the left atrium using a large bore catheter (e.g., EP procedures and/or other LAA devices such as WATCHMAN and Amulet).

These risks are well recognized and experienced clinicians that are well versed in the use of large bore catheters have mitigated these risks to the extent possible in their standard of care. The recognized procedural risks observed in prior studies with CLAAS and other LAAO products include (in alphabetical order):

- Acute Kidney Injury potentially requiring need for dialysis
- Air embolus
- Allergic reaction to contrast media necessary for imaging during procedure
- Anesthesia risks (e.g., nausea/vomiting, aspiration pneumonia)
- Arrhythmia
- Bleeding/anemia requiring transfusion
- Cardiac Perforation, Puncture, Tamponade, and/or Effusion requiring drainage and/or "open heart" surgery
- Chest pain/angina
- Damage to cardiac structure (e.g., valve, chordae)
- Death
- Deep Vein Thrombosis or Pulmonary Embolism
- Dyspnea
- Electrolyte imbalance
- Fever
- Heart Failure
- Hematuria
- Hemodynamic Instability (hypotension/hypertension)
- Hemothorax
- latrogenic ASD requiring treatment
- MI including ST segment elevation
- Pericardial Effusion/tamponade
- Pleural Effusion
- Pulmonary Edema
- Respiratory failure
- Stroke/TIA or Systemic embolization
- Systemic Infection including pneumonia
- TEE/intubation risks including throat pain, trauma to airway or esophagus with or without bleeding
- Thrombocytopenia
- Thromboembolic event

• Venous access site complications including pain, AV fistula, pseudoaneurysm, infection, hematoma, bleeding requiring transfusion and/or the need for surgical repair

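### The conscious-sedation sub-study's primary safety composite and its tested Procedure Success endpoint leave out all-cause death, major bleeding as such, serious sedation or airway events and conversion to general anesthesia, so they do not measure the sedation safety named in Objective 3

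*Protocol*

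**What the plan says.** Objective 3 (Protocol Section 8.1) is "To demonstrate the ability to safely deliver the CLAAS Device using a conscious sedation protocol without general anesthesia". Appendix E serves that objective with a single-arm sub-study compared with CLAAS subjects from the randomized trial.

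- **Primary safety (Appendix E, I.ii).** "A composite of Major Procedure-related complications assessed through 45 days (listed below"), counted "as adjudicated by an independent Clinical Events Committee as related to either the study device or procedure". The list is cardiac perforation, "pericardial effusion requiring drainage", ischemic stroke, device embolization and major vascular complications. No hypothesis, margin or threshold is attached.
- **Tested endpoint (Appendix E, I.i and J).** "The goal of the Sub-Study will be to demonstrate non-inferiority between the two procedural techniques based on the Procedure Success at 45-day endpoint". Success needs an acceptable implant position, closure or a leak of at most 5 mm on core-lab TEE at 45 days, and no major procedure-related complication in hospital or to day 7, whichever comes first.
- **Randomized trial's primary safety (Section 8.5.1).** The same five complications, plus "Major bleeding through 12 months post procedure or" "All-cause death 12 months post procedure".
- **Listed procedural risks (Section 12.7.1).** These include "Anesthesia risks (e.g., nausea/vomiting, aspiration pneumonia"), with respiratory failure and TEE or intubation injury as separate entries.
- **Conversion to general anesthesia.** Not mentioned anywhere, whether as a harm, a failure or a data item.

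**The concern.** The sub-study sets out to change one thing relative to the randomized CLAAS arm: the anesthesia method. Its primary safety result should therefore respond to harm that comes from that change. The five listed events are mainly consequences of catheter, device and access. Respiratory failure or aspiration under sedation belongs to none of them, and Appendix E gives no reason for dropping death and major bleeding, which the parent trial counts.

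Conversion raises a separate difficulty. Objective 3 concerns delivery without general anesthesia. Yet a subject converted to general anesthesia during the procedure, with a well-placed implant and a good 45-day TEE, meets every condition of Procedure Success.

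At stake is what a positive result would mean. The sub-study could report non-inferiority and a low primary safety rate while the evidence most relevant to sedation sits in general adverse event tables, without a prespecified comparison with the randomized arm.

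**Working it through.** **1. Endpoint content side by side**

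| Event | Randomized trial primary safety (8.5.1) | Sub-study primary safety (App. E, I.ii) | Procedure Success (App. E, I.i) |
|---|---|---|---|
| Five procedure-related complications | yes, 12 months | yes, 45 days | yes, in hospital or to day 7 |
| All-cause death | yes | no | not named; no 45-day TEE possible after earlier death |
| Major bleeding as such | yes | no | no |
| Serious sedation or airway event | not named | no | no |
| Conversion to general anesthesia | not named | no | no |

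Some deaths and bleeds enter indirectly. Appendix A counts a vascular injury that leads to death or to VARC type 2 or higher bleeding as a major vascular complication, and drained effusions overlap with tamponade.

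**2. The plan's own power figure**

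Inputs from Appendix E, J: 122 evaluable sedation subjects (130 enrolled, 6% attrition; 130 × 0.94 = 122.2), about 600 comparators, margin 0.10, one-sided alpha 0.05, anticipated success 90-95%, Farrington-Manning test.

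Power = Φ[(pt − pc + 0.10 − 1.645 × SE0) / SE1]. SE0 uses the proportions fitted under pt − pc = −0.10, and SE1 uses the assumed true rates.

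At pt = pc = 0.90:
- Fitted null proportions: 0.8098 and 0.9098.
- SE0 = √(0.8098 × 0.1902/122 + 0.9098 × 0.0902/600) = 0.0374.
- SE1 = √(0.09/122 + 0.09/600) = 0.0298.
- Power = Φ[(0.10 − 1.645 × 0.0374)/0.0298] = Φ(1.29) = 90.2%.

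The same calculation gives 94.6% at 92.5% success and 98.3% at 95%. The stated power of more than 90% reproduces, and no figure in Appendix E is wrong on this point.

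**3. How far the test responds to an uncounted harm**

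The Protocol gives no 45-day rate for death, bleeding, sedation harm or conversion, so this is an illustration. Assume that a fraction q of sedated subjects, in excess of the comparator, has a harm outside the five components and otherwise meets Procedure Success. As written, the chance of passing does not depend on q. If those subjects counted as failures, pt would become pc − q:

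| q | As written, 90% success | Counted, 90% success | As written, 95% success | Counted, 95% success |
|---|---|---|---|---|
| 1% | 90.2% | 82% | 98.3% | 94% |
| 2% | 90.2% | 72% | 98.3% | 85% |
| 3% | 90.2% | 60% | 98.3% | 73% |
| 5% | 90.2% | 36% | 98.3% | 44% |

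**4. What 122 subjects can show about a rare harm**

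For a true rate of 1% or 2%, the chance of at least one case is 1 − 0.99^122 = 71% or 1 − 0.98^122 = 92%. With no case, the one-sided 95% upper limit is 1 − 0.05^(1/122) = 2.4%. A sub-study of this size can describe such harms usefully if they are prespecified and counted.

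**The case against.** A reader might infer that these harms are counted nowhere. The documents do not support that. The sub-study follows the main protocol's requirements, adverse events are collected from consent (Section 12), all serious and all procedure-related events are reportable (Section 12.1), and adverse events are assessed before discharge, at day 7 and at day 45. Only conversion is absent altogether. This objection stands and limits the point to the primary endpoints.

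A reader might also say that every sedation harm listed in the Protocol is excluded. Section 12.7.1 lists anesthesia and respiratory risks as general procedural risks, not as sedation harms, and conversion is not on that list.

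Death before day 45 could be read as slipping out as attrition. Procedure Success needs a 45-day TEE result, so such a subject arguably fails already. The text does not say which, and missing-outcome rules commonly belong to the SAP, whose sub-study amendment is promised. A clarification is enough.

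It would be tempting to size the problem by moving a few assumed deaths from attrition to failure in the sedation group and reading the change as margin consumed. That is unsound: the death count has no source in the Protocol, and the same rule would apply to deaths among the roughly 600 comparators.

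Finally, Appendix E frames the comparison as one of device delivery, for which the five complications are a coherent, like-for-like set. That defends them as a delivery measure, but does not make them a measure of safety under sedation. The objection has most force on conversion. It cannot occur in a comparator treated under general anesthesia, so counting it as failure in the powered test would load one group only and cost power, as the table shows.

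**Conclusion.** The point holds as a matter of endpoint content. Neither sub-study primary endpoint names all-cause death, major bleeding as such, serious sedation or airway events, or conversion to general anesthesia, so the primary results do not measure the sedation-specific safety in Objective 3. Endpoint content is fixed in Appendix E, so the promised SAP amendment alone would not cure it.

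No effect size can be taken from the Protocol. The supportable statement is about sensitivity: the chance of passing stays at 90.2% to 98.3% regardless of uncounted harm, against 60% to 73% if a 3% excess were counted. That comparison assumes equal underlying success of 90% to 95%, 122 versus 600 subjects, and harms confined to subjects who would otherwise be successes. It should be changed before the sub-study opens, but it does not invalidate the sample size or the non-inferiority test.

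**What to change.** - **Appendix E, I.ii:** add all-cause death, major bleeding (BARC 3-5) and CEC-adjudicated serious sedation or airway events through 45 days. Report the composite beside the same composite in the randomized CLAAS arm.
- **Appendix E, I.i and J:** state that death before the 45-day TEE is a Procedure Success failure in both groups.
- **Conversion to general anesthesia:** record it, report its rate, and add a sensitivity analysis of Procedure Success that counts conversions as sedation failures. Leave the powered primary test otherwise unchanged.

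**Cost.** Widening the safety composite costs no power, because it carries no test. The work is Appendix E wording, one eCRF field, the SAP amendment already promised, and CEC review of a few more events. That review should be written in, since Section 13.2 assures adjudication only for potential endpoint events and others the sponsor selects. The reported safety rate may look slightly less favourable. If counting deaths lowers success equally in both groups, power falls somewhat (94.6% at 92.5% success, 90.2% at 90%). The check of the sample size against the observed CLAAS rate, already planned in Section 8.3.3, can absorb that. Enrollment waits for completion of the randomized trial and an IDE Supplement, so there is time to make the change.
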